	
1) presence of any ferromagnetic implant (cardiac pacemakers, aneurysm clip, etc.) (2) pregnancy (3) claustrophobia or anxiety disorder (4) history of vertigo (5) persons with diabetes mellitus (self-report or HbA1C \geq 6.5%) (6) Sickle cell disease (7) persons taking prescription medicine for hypertension (8) blood iron deficiency (Hb concentration $<$ 11 g/dL or Hct $<$ 32%) (9) If volunteering for MRI: history of kidney disease and/or eGFR $<$ 60. (10) Middle-ear disorder (11) double vision (12) Seizure disorder (13) Multiple myeloma (14) Solid organ transplant (15) History of severe hepatic disease/liver transplant/pending liver transplant

Interference	MR Imaging based on DGE
Measure	The area of hyperintense and the AUC between 2-5min of DGE
Patients	brain tumor patient treated at Zhujiang Hospital of Southern Medical University
Statistical Method	Differential test and Consistency analysis were used for statistical analysis

Background

The priority treatment of brain tumor is surgical resection. Recurrent malignant glioma is the most common and highly malignant primary brain tumor in adults. It mainly includes the pleomorphic glioblastoma (GBM) and anaplastic astrocytoma (AA). The average survival period of GBM is only 14.6 months [1], while the average lifetime of AA is only 2 to 3 years [1, 2]. Residual tumor and highly recurrence rate is the main reason. Besides, the feasibility of reoperation is extremely low. Moreover, progression-free survival (6-month progression-free survival (6M-PFS)) was only 15-21% of patients with recurrent glioma. The response rate of conventional chemotherapy was less than 15% in patients with recurrent glioma [1, 2]. Therefore, accurate clinical assessment of tumor scope is of great significance for GBM expansion surgery to remove the potential tumor immersed area and improve the survival rate of patients.

Recently, natural D-glucose suggested as a potential biodegradable contrast agent. The feasibility of using D-glucose for dynamic perfusion imaging explored to detect malignant brain tumors based on the breakdown of blood brain barrier (BBB)[3]. Our study try to evaluate the feasibility of dynamic glucose enhanced(DGE) magnetic resonance imaging (MRI) in brain tumor, which based on D-glucose weighted chemical exchange saturation transfer (glucoCEST).

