Time-resolved glucose signal changes were detected using chemical exchange saturation transfer (glucoCEST) MRI. Dynamic glucose enhanced (DGE) MRI was used to measure tissue response to an intravenous bolus of D-glucose. Starting the dynamic glucose scan, 3 minutes later, a brief hyperglycemic state was established by intravenous infusion of hospital-grade D50 glucose (D50, 25 g of dextrose in 50 mL of water sterile solution), followed by 20 mL of saline solution in 1 arm. The glucose infusion was performed using a power injector at an infusion rate of 0.2 mL/s, corresponding to total infusion times of 250 seconds. Performing dynamic contrast enhancement based on Gd-DTPA in 30 minutes later, which was used for comparison as golden standard. Dose of agent is according to the proportion of 0.2ml/kg body weight. The Gd-DTPA infusion was performed using a power injector at an infusion rate of 3 mL/s, followed by 20 mL of saline solution in 1 arm.

Statistic Analysis

Statistic tools: SPSS 23.0

Basic principles:

All statistical inferences were tested by bilateral tests, the test level of statistical significance was set at 0.05, and the confidence interval of parameters was estimated by 95% confidence interval. The parametric method is used as far as possible. When the data does not meet the parametric method conditions, the data transformation method can be used to make it meet the conditions. If the data still does not meet the parameter method conditions, the non-parametric method can be considered.

Missing data:

The case data that did not meet the statistical requirements were excluded.

Description statistics:

The mean, standard deviation and confidence interval are given for measurement data. The minimum, maximum, P25, median and P75 are given if necessary. The mean and standard deviation of the trip value were calculated from paired measurement data. Median and mean rank are given when nonparametric methods are used. The enumeration data give the frequency distribution and the corresponding percentages. Rank data give frequency distributions and corresponding percentages, as well as median and mean rank. The positive rate, positive number and the number of cases in the denominator were given in qualitative data.

Baseline data analysis:

Descriptive analysis of baseline data, including baseline levels of endogenous glucose CEST in brain tissue.

Analysis of influencing factors:

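### On the non-parametric route the protocol names median and mean rank, without saying whose median and without an estimate and interval that match a paired rank test

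*Protocol*

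**What the plan says.** The Methods of DGE section makes the comparison paired: "Performing dynamic contrast enhancement based on Gd-DTPA in 30 minutes later, which was used for comparison as golden standard". The Abstract gives the analysis in one line: "Differential test and Consistency analysis were used for statistical analysis". No specific test is named.

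Under Statistic Analysis, Basic principles, the order is parametric first, then transformation, and then: "If the data still does not meet the parameter method conditions, the non-parametric method can be considered". The same paragraph sets the general rule that "the confidence interval of parameters was estimated by 95% confidence interval".

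Three sentences under Description statistics bear on the point:

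- For continuous data in general: "The mean, standard deviation and confidence interval are given for measurement data".
- For paired data: "The mean and standard deviation of the trip value were calculated from paired measurement data". I read the garbled term as the difference value.
- For the fallback route: "Median and mean rank are given when nonparametric methods are used".

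The last is the only summary tied to the non-parametric route. It does not identify the variable whose median is meant, and it mentions no interval.

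**The concern.** The stated purpose is to learn whether glucose CEST imaging is superior to gadolinium imaging. For a measure taken on both scans, such as hyperintense area, the answer lies in the direction, size and precision of the within-patient difference.

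The summary named for the fallback route serves this poorly. A mean rank is unitless, depends on the number of pairs, and is not the quantity that a signed-rank test compares, which is the rank sum. A median per modality ignores the pairing. A median of the paired differences would be a usable size, but the sentence does not say that this is meant. None of these is given with the 95% interval that the Basic principles call for.

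At stake is a report in which a significant rank test stands beside figures that do not express what it found, or that seem to point the other way.

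**Working it through.** The protocol gives no figure on this point, so there is none to reproduce. The check asks whether the named summaries can disagree with the test.

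**Inputs**

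- n = 100 pairs (Abstract, Sample Capacity). Assumed: every patient contributes both scans and no difference is zero.
- Two-sided 0.05 (Basic principles), so the critical value is 1.96.
- Test: Wilcoxon signed-rank. This is an assumption, since the protocol names none.
- Mean rank: taken as the mean rank of the positive and of the negative differences, which is also an assumption.

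**1. The test statistic.** W+ is the number of positive differences times their mean rank. Without a true difference its mean is n(n+1)/4 = 100 × 101/4 = 2525. Its SD is √[n(n+1)(2n+1)/24] = √(100 × 101 × 201/24) = √84,587.5 = 290.8.

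**2. Equal mean ranks, significant test.** Take 65 positive and 35 negative differences, both with mean rank 50.5.

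- W+ = 65 × 50.5 = 3282.5
- z = (3282.5 − 2525)/290.8 = 2.60, two-sided p = 0.009

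Without ties, rank sums are whole numbers. Sums of 3282 and 1768 give mean ranks 3282/65 = 50.49 and 1768/35 = 50.51, and again z = 2.60. The mean ranks show no difference, while the test is clearly significant.

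**3. How lopsided the split must be.** Significance needs W+ above 2525 + 1.96 × 290.8 = 3095. At mean rank 50.5 that is 3095/50.5 = 61.3, so 62 positives of 100 suffice: 62 × 50.5 = 3131, z = 606/290.8 = 2.08. With 61, z = 555.5/290.8 = 1.91.

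**4. Reversed mean ranks.** A constructed set has 80 positive differences spread evenly from 0.1 to 2.0, and 20 negative ones between −1.5 and −2.1.

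- Rank sums: 3421 positive, 1629 negative (total 5050 = 100 × 101/2)
- z = (3421 − 2525)/290.8 = 3.08, p = 0.002, in favour of positive
- Mean ranks: 3421/80 = 42.8 positive, 1629/20 = 81.5 negative

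The mean ranks point against the test.

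**5. Whose median.** In the same set, the differences were added to reference values spaced from 5 to 25 in random order.

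| Summary | Value |
|---|---|
| Difference of the two modality medians | 14.81 − 15.00 = −0.19 |
| Median of the paired differences | +0.81 |
| Hodges-Lehmann estimate (95% CI) | +0.73 (0.38 to 0.94) |
| Mean paired difference (SD) | +0.48 (1.25) |

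The two readings of the word median give opposite signs. The Hodges-Lehmann estimate and the median of the differences agree in direction but are not the same number.

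**6. The mean difference.** Its 95% interval follows from the planned mean and SD: 0.48 ± 1.96 × 1.25/√100 = 0.48 ± 0.25, about 0.23 to 0.73. Its direction is right here, but its size is not the shift that the rank test assesses (0.48 against 0.73).

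Steps 2 to 6 show what can happen. They say nothing about how often.

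**The case against.** The strongest reply is that the sentence is generic. It stands under descriptive statistics, does not mention the DGE-Gd comparison, does not say that only these summaries are given, and would suit unpaired or ordinal data. The route is optional and comes after transformation, and an SAP that is not shown may name the estimator. All of this stands, and it keeps the point small. It does not remove it: the protocol does state a summary for this route, and an analyst who follows it would report mean ranks.

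Three stronger readings are tempting, and the documents do not support them.

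- A reader might infer that the paired difference is left with no size or interval. The protocol also plans the mean and SD of the paired difference, a confidence interval for continuous data and a 95% interval for parameters. None of these is limited to the parametric route. What is missing is an estimate and interval that match a rank test.
- A reader might infer that the plan prescribes modality medians. It does not say so. The sentence follows directly on the one about paired differences, so the median of those differences is a fair reading, and in the constructed set that median has the test's direction. The text is ambiguous here rather than wrong.
- A reader might infer that reversals would be frequent because tumour areas are skewed. If areas and their ratio are lognormal, the log ratio is normal, and the plan's transformation step would lead to a parametric paired test. Reversal rates from such a model do not describe trials that reach this route, and the documents give no data from which to estimate a rate.

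**Conclusion.** The point holds in a limited form. The summary tied to the non-parametric route is ambiguous about the median. It also includes mean ranks, which do not measure size, have no interval, and can be equal or reversed while a signed-rank test is significant (n = 100, 65 against 35 at mean rank 50.5: z = 2.60, p = 0.009). The planned mean and SD of the paired difference soften this but do not match a rank test.

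The conclusion rests on three assumptions: the rank test would be the signed-rank test, the compared measure is taken on both scans, and the garbled term for paired data means the difference. It applies only if both the parametric conditions and transformation fail. How often the summaries would mislead cannot be said from the documents. It is a reporting correction worth making, and no stated figure changes.

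**What to change.** Replace the sentence with wording such as: *When a non-parametric method is used for the paired DGE-Gd comparison, report the Hodges-Lehmann estimate of the within-patient difference (the median of the Walsh averages) with its 95% confidence interval from the signed-rank test. The sample median of the paired differences may be given as a separate description. Medians of each modality are descriptive only, and mean ranks are not used to describe size or direction.*

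The Hodges-Lehmann estimate and the sample median of the differences should be named separately. They diverge when differences are skewed, as in the constructed set (0.73 against 0.81), and the signed-rank interval belongs to the former.

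The cost is one sentence and one routine calculation on paired data already held. No patients, scans or procedures are added.
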